5.5 Subject withdrawal and termination

5.5.1 Potential reasons for withdrawal

In accordance with the Declaration of Helsinki and other applicable regulations, a subject has the right to withdraw from the study at any time and for any reason without prejudice to his or her future medical care. The Investigator or Medical Monitor may also withdraw the subject at any time if it is medically necessary or in the interest of subject safety.

A subject will be discontinued from this study if any of the following criteria are met:

1. Withdrawal of consent by the subject is received. In the opinion of the Investigator or Medical Monitor it is not in the subject's best interests to continue in the study.
2. Occurrence of an Adverse Event (AE) or Serious Adverse Event (SAE), which, in the opinion of the Investigator, warrants discontinuation of the subject from the study.
3. Pregnancy as informed by the subject or as determined by a positive urine pregnancy test.
4. Significant non-compliance with study procedures that would interfere with the study results or increase the subject's risks in the study, as determined by the Investigator.
5. Subject is deemed to be a treatment failure if upon revisit it is determined that they are still infested having live lice. They will be terminated from the study and provided the standard of care at that point in the study.
6. Any clinical adverse event (AE), laboratory abnormality, or other medical condition or situation occurs such that continued participation in the study would not be in the best interest of the participant.
7. The participant meets an exclusion criterion (either newly developed or not previously recognized) that precludes further study participation.

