Statistical Analysis	
ANALYSIS POPULATIONS
 
Safety Population includes all subjects receiving dispensed treatment. This is the population that will be used for the safety assessments.
 
Modified Intent-to-Treat (mITT) population includes all subjects who met all inclusion/exclusion criteria, were randomized, dispensed treatment, and had at least one post-treatment efficacy evaluation. This is the primary population for determination of the kill rate against head lice.
 
Per-Protocol (PP) population includes all subjects who received treatment, had no protocol deviations which could have interfered with the accurate assessment of treatment efficacy, and returned for the Day 14 visit within the allowed window. This population is the secondary analysis.
 
EFFICACY ANALYSIS
 
Primary Efficacy Endpoint The primary efficacy endpoint is the proportion of subjects who are lice free (defined as no live lice, adults or nymphs) 14 days after treatment.
 
Secondary Efficacy Endpoint The secondary efficacy endpoint is the number and percentage of all subjects who are lice-free at Day 2.
 
SAFETY ANALYSIS Descriptive statistics on the severity and duration of adverse events (AEs) from all subjects will be determined for any AE that occurs in at least 5% of the subjects.
 
Analysis of tolerability will be based on scores of Stinging/Burning and Itching sensations collected during Subject Self-Assessment and Source Document at all follow-up visits between the test and reference treatment groups.

PRINCIPAL CONTACTS	South Florida Family Health and Research Centers, LLC. DBA: Lice Cleanique [name], CEO [name] [contact] Mob.: [contact]

	[name], APRN, PI [name] [contact] [contact]
CLINICAL PROTOCOL AND CONDUCT INQUIRIES	Alliance Pharmaceuticals Ltd. [name] R&D Director [contact]
CLINICAL SAFETY INQUIRIES	Alliance Pharmaceuticals Ltd. [name] R&D Director [contact]
PROTOCOL DEVIATIONS	Alliance Pharmaceuticals Ltd. [name] R&D Director [contact]
IRB - Institutional Review Board:	Advarra IRB (Formerly Schulman IRB) [name] [contact] [contact]

2. Study Introduction

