5.4 Strategies for recruitment and retention

- Expected total number of screened subjects will be 64.
- Given a 10% screen failure rate, an anticipated number of enrolled subjects will be 58.
- Assumed dropout rate is 10%, an expected number of 52 subjects will complete the study.
- Source of subjects will be primarily from established patient data base, community at large, area schools and daycares, along with referrals by local healthcare centers to research site.
- Retention of subjects will be supported by thorough visit reminders and proper education on the study itself, including study duration, activities and responsibilities.

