7.1 Study procedures and evaluations

Informed Consent, Eligibility Criteria, Subject Demographics, hair type and Investigational Product Dispensation/ Application on Day 0.

Medical History, Vital signs, Physical Examination, Head Lice Visual Assessment, Local Skin/Scalp Irritation Assessment, Ocular Irritation Assessment and Adverse Events Assessment will be collected at Baseline Visit 1 (post treatment), Visit 2, visit 3 and Final Study Visit 4.

Basic demographic information, including date of birth, sex, ethnicity, and race will be recorded at the Screening /Baseline Visits. Relevant medical history, and past history of head lice will be documented. All medications (both prescription and

nonprescription), including vitamins, herbals, topical, inhaled, and intranasal taken within 30 days prior to the start of the Study Drug and through the final study visit will be recorded on the appropriate source document (using their generic and/or brand names), if known with the corresponding indication, start and stop dates. At each study visit, subjects will be asked whether they have started or discontinued any medication since their previous study visit. This includes single use or PRN (as needed medication use).

Vital signs will include body temperature, heart rate and blood pressure (systolic and diastolic). Blood pressure and pulse rate will be measured after the subject has been sitting restfully for at least 5 minutes. Any abnormal characteristics of vital signs will be evaluated by the Investigator based on their significance. Any abnormal vital signs will be considered AEs if they require therapeutic medical intervention, and/or if the Investigator considers them to be AEs based on his/her clinical judgement.

Physical examination, including height, weight, and evaluation of organs and systems (General Appearance, Heart/Cardiovascular, Lungs, Gastrointestinal, Ears / Nose / Throat, Extremities, and Skin) will be assessed at Visit 1 Day 0, Visit Day 2, Visit Day 7, and Final Study Visit Day 14

Urine Pregnancy Test and Concomitant/ Prohibited Medication Review will be performed on all Visits.

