7.3 Study schedule

7.3.1 Screening/randomization

Screening Visit Day 0 (Visit 1)

- Obtain informed consent of potential participant verified by signature on written informed consent.
- Record demographic information, obtain medical history, and history of head lice.
- Review medications history and concomitant/prohibited medications to determine eligibility
- Verify inclusion/exclusion criteria.
- Collect urine sample for pregnancy testing for all subjects of childbearing potential.
- Perform assessment for living head lice on subjects and household members for a minimum of 15 minutes. Each subject must have at least 1 live louse. Rate severity of infestation. After each subject has been identified, additional infested household members will also be assessed for infestation.
- Level of infestation will be rated as heavy, moderate or light described by how quickly lice were found during combing: heavy infestation = >1 louse with one stroke of the comb; moderate infestation = 1 louse with one stroke of the comb; light infestation = first louse found only after several strokes of the comb
- Household members must have an active head lice infestation defined as: At least 1 live lice (adult and/or nymph) present on the scalp and/or hair, as determined by a trained evaluator. Household members will be assigned to the same study group as index case.
- Schedule study visits for participants who are eligible and available for the duration of the study.
- Randomly assign subjects to treatment or control group based on infestation severity alternation system (i.e., randomly assign pairs of equal severity levels to treatment and control groups, a form of stratified random sampling) to achieve balanced representation of severity in the two groups.
- Investigational Product Dispensation/ Application for subject.
- Provide each subject with homecare instructions including combing after first wash out.
- Inform subject when to come back for each follow-up visit.
- Provide Standard of Care treatment on-site to unqualified infested household members.

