10.2 Data sets to be evaluated

The subject populations are defined as follows:

Safety Population includes all subjects who were administered treatment. This is the population that will be used for the safety assessments.

Modified Intent-to-Treat (mITT) population includes all subjects who met all inclusion/exclusion criteria, were randomized, administered treatment, and had at least one post-treatment efficacy evaluation. This is the primary population for determination of the effectiveness of the active treatment.

Per-Protocol (PP) population includes all mITT subjects who were administered treatment, had no protocol deviations which could have interfered with the accurate assessment of treatment efficacy, and returned for the Day 14 visit within the allowed window. This is the primary population for the efficacy comparisons between the two active treatment groups.

Subjects whose condition worsens and require alternate or supplemental therapy for the treatment of head lice during the study will be discontinued, included in both the mITT and PP population analyses as treatment failures. Subjects who discontinue early for reasons other than treatment failure will be excluded from the PP population, but included in the mITT population, using Last Observation Carried Forward (LOCF).

Efficacy analyses will be performed on both the per-protocol population and the mITT population. Safety analyses will be performed using the Safety population as defined.

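### Subjects withdrawn for an adverse event, pregnancy or significant non-compliance leave the study, not only the product, so their Day 14 louse result is imputed in the mITT when it could be observed (minor)

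*Combined protocol and SAP*

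**What the plan says.** **Leaving the study.** Section 5.5.1 lists criteria under which a subject is discontinued from the study. Three matter here: an adverse event that in the investigator's opinion "warrants discontinuation of the subject from the study", pregnancy, and significant non-compliance. The synopsis repeats the first two, and 8.4.6 repeats pregnancy. Significant non-compliance appears in 5.5.1 alone. Section 5.5.2, although titled for the handling of withdrawals, covers only a sponsor decision to stop the trial. Section 5.6 asks for an end-of-treatment or discontinuation visit when a subject withdraws. No section keeps these subjects on the Day 7 and Day 14 louse assessments.

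**Product.** Application is on Day 0, with a repeat on Day 7 only if live lice are present (4.1, 7.3.3, schedule in 16.1).

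**Analysis.** The primary endpoint is lice-free status at Day 14 (4.2.2). Under 10.2, subjects who stop early for reasons other than treatment failure are "excluded from the PP population, but included in the mITT population, using Last Observation Carried Forward (LOCF"). Entry to the mITT requires that a subject "had at least one post-treatment efficacy evaluation". The synopsis says of the mITT: "This is the primary population for determination of the kill rate against head lice". Section 10.2 says of the PP population: "This is the primary population for the efficacy comparisons between the two active treatment groups".

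**Dropout.** Section 5.4 states: "Assumed dropout rate is 10%, an expected number of 52 subjects will complete the study". Section 10.5 turns this into an allowance of 3 per group. Neither section splits it by reason.

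**The concern.** Withholding product from a withdrawn subject prevents at most one further application. Withdrawing the subject from the study also ends the scheduled louse, scalp and ocular assessments. General adverse-event follow-up continues under 8.1, so safety follow-up as such is not lost. What is lost is the scheduled tolerability grading and the primary endpoint.

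The missing endpoint is then replaced by the last reading, most likely from Day 2, Day 7 or the 5.6 exit visit. The pilot described in 10.5 gives a reason to distrust that substitution: after a single application of the spray, 88% were lice free at Day 0 and 12% at Day 14. A subject who leaves while clear is counted as a Day 14 success, and also misses the Day 7 check that could have led to re-treatment.

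The PP analysis does not repair this, because it excludes the same subjects. The exit visit does not repair it either, because it supplies the value to be carried and not the Day 14 value. At stake is how far the mITT Day 14 comparison depends on when withdrawn subjects leave and from which arm.

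**Working it through.** **1. The plan's own sample size.** Inputs from 10.5: 45% against 85%, two-sided alpha 0.05, power 80%, 1:1. The uncorrected two-proportion formula gives 22 per group. With the continuity correction it gives 26 per group, N = 52, which matches the plan. With 10% dropout, 26 / 0.9 = 28.9, rounded up to 29 per group, 58 in total, which also matches. The dropout allowance is therefore 29 − 26 = 3 per arm, for all causes.

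**2. Shift in one arm's Day 14 rate under LOCF.** For k of 29 subjects carried forward, with carried readings clear at rate c and true Day 14 rate p for those subjects:

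shift = (k / 29) × (c − p)

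Assume c = 0.88, the pilot's Day 0 figure.

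| Dropouts in the arm | p = 0.12 | p = 0.45 | p = 0.85 |
|---|---|---|---|
| 1 | 2.6 points | 1.5 points | 0.1 points |
| 3 | 7.9 points | 4.4 points | 0.3 points |

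For example, 3/29 × (0.88 − 0.45) = 0.044.

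**3. Chance of a false spray win.** Exact binomial enumeration with 29 per arm. The test follows 10.1: pooled Z at two-sided 0.05, replaced by Fisher's exact test (one of the two options that 10.1 names) when either arm has fewer than 10 lice-free subjects. The true Day 14 rate is 45% in both arms. Observed subjects are clear at 45%, and carried-forward subjects at 88% unless stated. A win means significant in favour of spray, so the nominal level is 2.5%.

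| Dropouts carried forward | False spray win |
|---|---|
| None | 1.7% |
| One, spray only | 2.2% |
| Two, spray only | 2.9% |
| Three, spray only | 3.8% |
| Two spray, one control | 2.2% |
| Three per arm, both 88% clear | 1.7% |
| Three per arm, spray 88%, control 45% | 3.8% |
| Three per arm, spray 88%, control 100% | 1.3% |
| Three, spray only, all carried with live lice | 0.5% |

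**4. Total two-sided rejection.** With no dropouts it is 2 × 1.7% = 3.4% by symmetry. With three spray-only dropouts it is 4.5% under the 10.1 test, still below 5%. The plain pooled Z, without the switch to Fisher's test, gives 5.7% in that case.

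**5. What drives the result.** The error rate rises only when losses, or the status carried forward, differ between arms. Equal losses with equal clearance leave it where it started.

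**The case against.** The strongest case on the other side is that little harm is shown. The documents give no rate for withdrawal due to adverse events, pregnancy or non-compliance. Reaching 3.8% means attributing an arm's whole all-cause allowance of three to these reasons, and also having losses or carried status differ by arm. This stands, and it is why the point is minor.

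It is also fair to say that the adverse-event criterion covers only events the investigator thinks warrant leaving the study, and that 10.4.3 plans a summary of events leading to discontinuation of study drug. The protocol therefore recognises stopping drug as a category. It gives no procedure for keeping such a subject on visits, so the gap remains.

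The pilot comparison is close to a worst case. It used one application, whereas this trial repeats on Day 7 if lice persist, and it gives no Day 2 or Day 7 rate. A clear Day 7 check may predict Day 14 much better than a Day 0 check. This stands.

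A reader might go further in three ways that the documents do not support:

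- **Day 0 readings carried to Day 14.** Section 7.1 says that "Head Lice Visual Assessment, Local Skin/Scalp Irritation Assessment, Ocular Irritation Assessment and Adverse Events Assessment will be collected at Baseline Visit 1 (post treatment"). But the same label covers medical history and vital signs, 4.1 and 7.3.1 place the louse check in baseline screening before application, and the spray is washed out at home after 8 hours. A Day 0 carry-forward cannot be excluded, but it is not the likely case.
- **Whole households lost from one arm after a positive pregnancy test.** Section 7.3.1 says "Household members will be assigned to the same study group as index case", and 7.2.1 disqualifies the household. That sentence directly follows the requirement for a negative baseline result, so it reads most naturally as an eligibility rule.
- **Replacing LOCF by scoring missing results as failures.** This is not shown to be better. Its worst case is similar (3.3% with three control-only dropouts). At 85% against 45%, power with three dropouts per arm is 82.7%, against 85.4% under LOCF; with three spray-only dropouts it is 69.7%, against 91.6%.

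**Conclusion.** The point holds as a minor one. The protocol ends study participation where stopping product would do, and so imputes a primary endpoint that could have been observed at visits already on the schedule.

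On the illustration above, the chance of a false spray win moves from 1.7% to between 2.2% and 3.8% with one to three spray-only dropouts, and stays at 1.7% with balanced dropout at equal clearance. This rests on four assumptions: carried readings behave like the pilot's Day 0 result; 88% also applies to permethrin where both arms lose subjects, although no document gives that rate; clear dropouts receive no Day 7 repeat; and Fisher's test is used below 10 lice-free subjects.

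A reader might infer that the plan favours spray or breaks its 5% error rate. Neither follows. The direction is unknown, since spray dropouts carried with live lice push the result the other way, and total rejection under the 10.1 test stays at 4.5% even with three spray-only dropouts. The imputation affects only the mITT. The synopsis treats the mITT as primary, while 10.2 names the PP population for the between-group comparison.

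**What to change.** In 5.5.1, the synopsis and 8.4.6, separate two decisions: no further study product, and withdrawal from the study. Leave every rule on when product stops as it is. Unless consent is withdrawn, or the investigator judges further visits unsafe, keep these subjects on the scheduled Day 7 and Day 14 louse, scalp, ocular and adverse-event assessments.

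In 10.2, say that the observed Day 14 result is used in the mITT when it exists. A retained subject who needs other lice treatment first is scored as a failure, as 10.2 already provides. Say also that stopping product for these reasons still counts as early discontinuation for the PP population, so PP membership does not change.

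**Cost.** Wording in four places, and in the consent form if it describes withdrawal. No new visits and no change in sample size. Retained subjects carry a small visit burden, and some withdrawn for non-compliance will not attend, so LOCF will still be needed for a few.

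Observed results can also be less favourable than carried ones. At 85% against 45%, three retained spray subjects give power of 73.4% if their Day 14 rate is the pilot's 12%, and 91.0% if it is 85%, against 91.6% when they are carried forward at 88% clear. A loss of that kind would reflect what happened to those subjects and is not a reason to impute.

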At day 7, if live lice are still present, a repeat treatment will be administered. After day 7 if a subject reports clear signs of infestation (i.e., the presence of live lice), they will be regarded as a treatment failure and they will be offered treatment with an alternative product (viz., Vamousse Mousse) by clinical staff.

For the treatment group, Clinical staff will apply Vamousse Spray 'n' Go to fully coat dry hair and scalp, avoiding the eyes and mucus membranes. The Treatment will be left on the hair and scalp for 8 hours, then standard at home shampoo and rinsed off with warm water, followed by combing. The Treatment spray bottle is intended for a single use although it contains a sufficient quantity for two treatments. All household members will be instructed on an overall lice management program, which includes:

- Wash (in hot water) or dry-clean all recently worn clothing, hats, used bedding and towels.
- Wash (in hot water) personal care items such as combs, brushes and hair clips.
- Record time and date product shampoo/rinse 8 hours post treatment

For the control group, Clinical staff will first shampoo the hair and scalp using regular shampoo. They will then

thoroughly rinse and towel dry the hair and scalp, and allow hair to air dry for a few minutes. Shaking the permethrin lotion well before applying, they will proceed to thoroughly wet the hair and scalp with the permethrin lotion, being sure also to cover the areas behind the ears and on the back of the neck. After allowing the lotion to remain in place for 10 minutes, they will then rinse the hair and scalp thoroughly and dry with a clean towel.

The site will provide Subject with lice management instructions. Subjects will return for post-baseline visits assessments at Day 2, Day 7, and Day 14.

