Day 2: The Investigator and medical staff will collect medical history, collect vital signs, perform physical examination, scalp irritation assessment, ocular irritation assessment and adverse events assessment, perform a visual assessment for the presence or absence of head lice, (Lice will be counted, each stage examined and noted live or dead; 15in led 5x magnifying procedure lamp or laboratory microscopes are used for confirmation if needed, Without clipping hair strands, nits will also be examined, each stage examined and noted hatched or unhatched), and adverse events assessment Urine pregnancy testing will be performed on each Visit, with interim visits confirming pregnancy has not occurred through questioning participating subject and legal guardian.

Day 7: The Investigator and medical staff will collect medical history, collect vital signs, perform a physical examination, assess scalp irritation, assess ocular irritation and adverse events, perform a visual assessment for the presence of head lice (lice will be counted, each stage identified, and noted live or dead; 15in led 5x magnifying procedure lamp or laboratory microscopes will be used for confirmation if needed; without clipping hair strands, nits will also be examined, each stage examined, and noted hatched or unhatched). Urine pregnancy testing of females will be performed on each visit, with interim visits confirming pregnancy has not occurred through questioning participating subject and legal guardian. If, at day 7, live lice are still present, a repeat Vamousse Spray 'n' Go or Permethrin (depending on study group) shampoo treatment will be administered.

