Day 14: The Investigator and medical staff will collect medical history, concomitant and prohibited medication review, perform vital signs, urine pregnancy testing if applicable, perform physical examination, record local application site reactions, ocular irritation assessment, perform a visual assessment for the presence of head lice (lice will be removed, counted, each stage examined and noted live or dead; 15 inch led 5x magnifying procedure lamp or laboratory microscopes are used for confirmation; nits will also be removed by clipping hair strands, examined, each stage counted, and noted as hatched or unhatched) and adverse events assessment. By day 14 if a subject reports clear signs of infestation (i.e., the presence of live lice) they will be regarded as a treatment failure and will be offered treatment with an alternative product (Vamousse Mousse) by clinical staff.

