4.2.3 Secondary Endpoints

- Assessment of infestations detected: number of live adult and nymph forms at the 7-day visit confirmed by investigator inspection during detection combing.
- Proportion of subjects requiring re-treatment at 7 days.
- Proportion lice free at day 2 (i.e., 24 hours after first treatment)
- Volume of product used in relation to hair type (Volume will be weighted pre and post and weight will be recorded on the product log. Hair type will be recorded as fine, medium or coarse on source document.)
- Safety of the product – as determined by reported adverse events during the study and recalled at the end of the treatment period.
- Cosmetic acceptability of the product in daily use as determined by consumer assessment questionnaire at the 14-day visit.
- The mean change between day 14 and baseline in the counts of live lice (i.e., total of live adult lice and nymphs) in each study group (i.e., treatment and control).

5. Study Enrollment and Withdrawal

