7.3.2 Follow up

Follow-up Visit (Day 2) Visit 2 (+24hrs.)

- Medical History, Vital Signs, Physical Examination, Head Lice Visual Assessment, Local Skin/Scalp Irritation, Assessment, Ocular Irritation Assessment. Record results on Source Document.
- Record adverse events as reported by participant or observed by investigator.
- Record subject's adherence to homecare instructions.
- Perform assessment for living head lice on subject for visual confirmation of infestation.
- Record subject's adherence to homecare instructions.
- Inform each subject when to come back for their visit (Day 7) Visit 3 ± 1 days

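### Section 5.5.1 item 5 ends participation at any revisit with live lice, which contradicts the Day 7 repeat dose that the rest of the protocol prescribes

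*Combined protocol and SAP*

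**What the plan says.** Section 5.5.1 lists criteria under which a subject will be discontinued. Item 5 is one of them: "Subject is deemed to be a treatment failure if upon revisit it is determined that they are still infested having live lice". The consequence follows: "They will be terminated from the study and provided the standard of care at that point in the study". No visit is named.

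Other sections describe a different path for the same subjects.

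- Section 4.1: "At day 7, if live lice are still present, a repeat treatment will be administered". The Day 7 paragraph of that section specifies the assigned product in each arm: "a repeat Vamousse Spray 'n' Go or Permethrin (depending on study group) shampoo treatment will be administered".
- Section 7.3.3 repeats the instruction and then books the Day 14 visit. Section 16.1 allows product at Visit 3 if needed.
- Section 3 includes re-application after 7 days among the questions to be studied, and Section 4.2.3 has the endpoint "Proportion of subjects requiring re-treatment at 7 days".
- Section 7.3.2 (Day 2) books every subject for Day 7 and provides no exit for live lice.
- Treatment failure is placed later. Section 4.1 begins one rule "After day 7 if a subject reports clear signs of infestation" and another "By day 14 if a subject reports clear signs of infestation"; Section 7.6 ties failure and rescue to live lice on Day 14.
- The synopsis list of discontinuation criteria has no live-lice item.

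**The concern.** A subject with live lice at Day 7 is, under item 5, a failure who leaves the trial for standard of care. Under Sections 4.1 and 7.3.3 the same subject is re-dosed, followed for another week, and may be a success on the primary endpoint. The endpoint itself, lice free at Day 14, is defined consistently. The conflict lies in the rule that decides who reaches Day 14 and who has already been counted as a failure.

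Two things are at stake. First, the regimen under test: if item 5 is obeyed, nobody receives the second dose, and the trial evaluates a single application. Second, the responder count: it depends on which section staff follow. The trial is open-label, so staff choosing between two valid instructions know which product the subject received and could choose differently by arm.

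**Working it through.** **Which subjects are affected.** Post-baseline visits are Day 2, Day 7 and Day 14 (Section 4.1).

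| Live lice found at | Section 5.5.1 item 5 | Rest of the protocol |
|---|---|---|
| Day 2 | failure, terminated, standard of care | continues to Day 7 (7.3.2) |
| Day 7 | failure, terminated, standard of care | repeat of assigned product, continues to Day 14 (4.1, 7.3.3, 16.1) |
| Day 14 | failure, standard of care | failure, Vamousse Mousse (4.1, 7.6) |

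The rules agree on failure only at Day 14, and even there they name the follow-on treatment differently. Eligibility for the repeat dose is live lice at Day 7, which is also item 5's trigger, so under item 5 the re-treated group is empty.

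**The plan's sample size.** Inputs from Section 10.5: p1 = 0.45, p2 = 0.85, two-sided alpha 0.05, power 0.80, allocation 1:1. With mean proportion 0.65:

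n = [1.96·√(2·0.65·0.35) + 0.842·√(0.45·0.55 + 0.85·0.15)]² / 0.40² = 21.1, or 22 per group.

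With the continuity correction, n′ = (n/4)·[1 + √(1 + 4/(n·0.40))]² = 25.9, or 26 per group and 52 in total. This matches the plan. Dropout: 26/0.90 = 28.9, so 29 per group and 58 in total. The arithmetic is not in dispute.

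**What the effect rests on.** The 85% versus 45% comes from a trial of a different spray. For this product, Section 10.5 reports a once-only pilot with 88% lice free at day 0 after treatment and 12% at day 14, and expects the Day 7 repeat to bring Day 14 back to about the day 0 level.

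**Sensitivity of power.** The documents give neither arm's Day 14 rate under item 5, so the losses below are assumptions. For each pair of rates, the probability of rejection is the sum of Bin(a; 26, p_control)·Bin(b; 26, p_spray) over all outcomes (a, b) where the two-sided pooled Z test gives |Z| > 1.96. The last column applies Fisher's exact test whenever either group has fewer than 10 lice-free subjects, one of the alternatives Section 10.1 allows.

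| Assumed effect of item 5 | Spray | Control | Pooled Z | With Fisher switch |
|---|---|---|---|---|
| none (plan) | 85% | 45% | 89% | 89% |
| spray loses 10 points | 75% | 45% | 62% | 61% |
| spray loses 20 | 65% | 45% | 30% | 27% |
| spray loses 30 | 55% | 45% | 10% | 8% |
| spray loses 20, control 10 | 65% | 35% | 57% | 51% |
| both lose 10 | 75% | 35% | 84% | 82% |
| both lose 20 | 65% | 25% | 84% | 78% |
| both lose 30 | 55% | 15% | 89% | 82% |

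**An extreme case.** Suppose the spray falls to the pilot's 12% and control stays at 45%. The null standard error is √(2·0.285·0.715/26) = 0.125 and the alternative one is √((0.12·0.88 + 0.45·0.55)/26) = 0.117. The chance of a significant result favouring control is Φ((0.33 − 1.96·0.125)/0.117), about 77%, and the chance of one favouring the spray is practically nil. This is not a forecast: control subjects would lose their repeat dose too.

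**The case against.** The strongest reply is that the intended rule is plain. The Day 7 repeat appears in the objectives, the design, the visit procedures, a secondary endpoint, the sample size rationale and the schedule of events. Item 5 stands alone and looks like a stray clause. Staff would probably follow the visit schedule, so total loss of the repeat dose is the literal worst case and not the likely conduct. The trial has one centre, and neither rule distinguishes the arms, so uneven application by arm is a possibility without direct evidence. The power losses are all assumed, and their range includes almost no loss.

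Most of this is fair, and it makes the correction easy to identify. It does not dispose of the point: item 5 is mandatory, no section overrides it, and following either instruction breaches the other for the very subjects who decide the primary result.

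Three narrower objections also have some force. The pooled Z figures ignore the small-count rule in Section 10.1, but applying Fisher's test there lowers them only modestly. No section says outright that live lice at Day 2 leave participation unchanged; that follows from Section 7.3.2 booking Day 7 and Section 4.1 re-treating lice that persist to Day 7. Section 10.2 is ambiguous and not contradictory: it concerns subjects who worsen and need other therapy, so its change is a clarification.

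**Conclusion.** The concern holds. This is an internal contradiction in the discontinuation and failure rule, established by the text alone, and it should be corrected before enrolment. It decides whether a second dose is given at all and whether subjects with live lice at Day 2 or Day 7 can still count as Day 14 successes.

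The numerical effect cannot be fixed from the documents. It runs from small, if both arms depend equally on the repeat dose, to nearly complete loss of power, if only the spray does. The pilot's 12% at day 14 shows why Section 10.5 needs the second dose, but it does not settle the difference between arms.

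**What to change.** Replace Section 5.5.1 item 5 with:

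> Live lice at Day 2 do not end participation. Live lice at Day 7 lead to one repeat dose of the assigned product (Section 7.3.3). Live lice found after the Day 7 visit or at Day 14 are a treatment failure, with rescue under Section 7.6.

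Add to Section 10.2, as clarification:

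> The protocol-specified Day 7 repeat of the assigned product is not alternate or supplemental therapy. A re-treated subject who is lice free at Day 14 counts as a success, in both arms.

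The cost is a wording amendment with IRB approval before enrolment. The sample size stays at 52 evaluable and 58 enrolled, and no visits or procedures are added.
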